1 PROTOCOL SUMMARY

1.1 SYNOPSIS

Title: Boost rTMS for AVH – Therapeutic Response and Neurobiological Prediction Markers in Auditory Verbal Hallucinations

Study Description: This is a randomized, placebo controlled, double-blind clinical trial. We aim to examine the efficacy of repeated transcranial magnetic stimulation (rTMS) for the treatment of auditory verbal hallucinations (AVH) in patients with schizophrenia who are not taking antipsychotic medication. We employ a novel, accelerated protocol with only 4 sessions of low-frequency rTMS in one day. The effects of this accelerated protocol will be compared to the sham stimulation. Additionally, we will examine the effects of rTMS on a neurophysiological level by evaluation mechanism of action in the temporo-parietal lobe.

Objectives: Primary Objective:
Examine the efficacy of low-frequency rTMS for AVH in patients with a schizophrenia spectrum disorder.

Secondary Objectives:
Examine the effects of rTMS on the quality of AVH, positive symptoms, general psychopathology, and the global level of functioning of these patients. Last, confirm that rTMS has no side effects on cognitive functioning.

Determine the neuroimaging-related biomarkers associated with response to rTMS using the baseline imaging parameters (rCBF, resting fMRI, T1, and DTI) to predict response to rTMS treatment. Further,

compare pre- and post-treatment imaging parameters (rCBF, resting fMRI, T1, and DTI) to characterize rTMS effects on AVH.

Endpoints:

Primary Endpoint:

- AVH assessed using the Hallucination Change Scale (HCS) at baseline (first visit), after the last TMS session, after the post-MRI.

Secondary Endpoints:

- a) Assessment of the qualitative content of hallucinations will be assessed using the revised Beliefs About Voices Questionnaire (BAVQ-R)
- b) Assessment of AVH as part of positive symptoms will be assessed with the Brief Psychiatric Rating Scale (BPRS)-subscale that includes "Hallucinatory Behavior", "Conceptual Disorganization", "Suspiciousness", and "Unusual Thought Content".
- c) Global functioning will be assessed using the Clinical Global Impression (CGI) and General Assessment of Functioning (GAF) questionnaires.
- d) Cognitive functioning will be assessed using the Repeatable Battery for the Assessment of Neuropsychological Status (rBANS).

Neurophysiological changes using magnetic resonance imaging (MRI) are investigated as predictors for rTMS treatment response.

Study Population:

N = 40

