- Male and female subjects 18 to 65 years of age
- DSM V diagnosis of schizophrenia (295.90), schizoaffective disorder (295.70) or brief psychotic disorder (298.80) confirmed by SCID-V interview currently experiencing AVH in the acute phases of the disorder as assessed with the revised Beliefs About Voices Questionnaire (BAVQ-R).
- Patient agrees to rTMS for AVH treatment for 1 day before standard medication therapy.
- Right-handedness assessed with the Edinburgh Handedness Inventory
- Patient is competent to provide informed consent
- Inpatient at the Zucker Hillside Hospital
- No history of seizures

Phase:

N/A

**Description of
Sites/Facilities Enrolling
Participants:**

Participants will be recruited through the Zucker Hillside Hospital in-patient clinic. Recruitment will only take place at this site and no sites outside of the United States are included.

**Description of Study
Intervention:**

All patients receive 1Hz of rTMS over the Sylvian parietal temporal area (area Spt) four times on 1 day (1 pulse/second and a total of 1'000 pulses: 16 minutes' protocol at 100% of motor threshold modified based on

Hoffman et al. (1999)). Area Spt will be localized via baseline structural imaging and our Localite TMS navigation system.

Subjects will be withdrawn from the study if side effects become limiting, or if either the patient or principal investigator determine that rTMS should be discontinued.

[figure not shown]
Study Duration: 18 months in total including 12 months for recruitment and measurements plus 6 months for data analysis.

Participant Duration: Each participant is enrolled for up to 4 days of measurements (minimum of 3 days).

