If the total payment received from Northwell Health, during this year, is equal to \$600 or more, the payment is required to be reported to the IRS. Although this study does not pay \$600, if patients participate in other Northwell Health studies, it is possible their payment could end up totaling \$600. If this occurs, the payment received on this study will be reported to the IRS. In this case, patients will be issued a 1099 form and be required to provide their social security number at that time for reporting purposes. Patients will also be responsible for reporting this income while filing your tax return.

Compensation

	Screening Day	Baseline Assessment	Treatment Day	Follow-up Assessment
Visits	Visit 1	Visit 2	Visit 3	Visit 4
Procedures				
rTMS	None	None	Any weekday	None
MRI	None	1 st at baseline	None	2 nd after rTMS
Clinical Assessment & blood work	Yes	Yes	Yes	Yes
Compensation	\$20	\$50	\$0	\$50

Note that the Screening Day is not specifically set. This day can either be on the first day of the study such that patients who are willing to participate could start immediately with the baseline measurements. While patients who are for example recruited in the evening would have their first day of the study on the following day. In the special case of enrollment on a Friday, the start of the study would be the following Monday. Thus, patients would have to declare that they do not want to take antipsychotics during the weekend and the time of the study. See section 2.3.1 “Known Potential Risks” for information.

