6.1.2 DOSING AND ADMINISTRATION

All patients receive 1Hz of rTMS over the area Spt four times on 1 day (1 pulse/second and a total of 1'000 pulses: 16 minutes' protocol at 100 % of motor threshold modified based on Hoffman et al.(Hoffman et al., 2003)). Area Spt will be localized via baseline structural imaging and our Localite TMS navigation system. Subjects will be withdrawn from the study if side effects become limiting, or if either the patient or principal investigator determine that rTMS should be discontinued.

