6.4 STUDY INTERVENTION COMPLIANCE

Compliance to study intervention is firstly confirmed by the patient signing the informed consent form. If patients do not want to continue treatment and finish all 4 rTMS sessions together with pre- and post-imaging and interviews, they will be excluded from the study which will be mentioned in the case report form. The data collected up to this point will not be included in the analysis because the primary outcome is the outcome measure of the HCS for which all three measures (baseline, after the last rTMS session, post-MRI) are necessary to reasonably estimate the symptom trajectory.

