7 STUDY INTERVENTION DISCONTINUATION AND PARTICIPANT DISCONTINUATION/WITHDRAWAL

7.1 DISCONTINUATION OF STUDY INTERVENTION

Discontinuation from rTMS does not mean discontinuation from the study, and remaining study procedures should be completed as indicated by the study protocol. If a clinically significant finding is identified (including, but not limited to changes from baseline indicated by a score of 3 (“mild”) or less for all four items of the positive symptom BPRS-subscale (Robinson et al., 2015)) after enrollment, the investigator or qualified designee will determine if any change in participant management is needed. Any new clinically relevant finding will be reported as an adverse event (AE).

The data to be collected at the time of study intervention discontinuation will include the following:

- Reason for discontinuation
- Positive symptoms BPRS-subscale rating
- BAVQ-R rating
- MRI measurements

The specimens of individuals for whom an extra vial of blood was extracted for potential serum antipsychotic concentration analysis that later do not consent to participate in the study will be destroyed immediately without being processed.

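### Section 7.1 leaves the primary outcome (HCS) off its list of data to collect when rTMS is stopped, and other sections withdraw the patient whom 7.1 keeps in, so a post-baseline HCS is possible but not assured for an early stopper

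*Combined protocol and SAP*

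**What the plan says.** On a patient who stops treatment early, section 7.1 states: "Discontinuation from rTMS does not mean discontinuation from the study, and remaining study procedures should be completed as indicated by the study protocol". Its list, opened by "The data to be collected at the time of study intervention discontinuation will include the following", has four entries: the reason, the BPRS positive-symptom subscale, the BAVQ-R and MRI. The HCS, which section 3 makes the primary outcome, is not among them.

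Other sections treat the same event differently:

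- Sections 1.1 and 6.1.2 share one sentence. It begins "Subjects will be withdrawn from the study if side effects become limiting" and continues "or if either the patient or principal investigator determine that rTMS should be discontinued".
- Section 6.4 says of patients who do not want to continue and finish that "they will be excluded from the study which will be mentioned in the case report form", and adds: "The data collected up to this point will not be included in the analysis".
- Section 7.2 lets the investigator withdraw a patient who cannot receive all four sessions, or who has side effects that he or she will not tolerate.
- Section 8.3.5 withdraws a patient with an adverse event that is serious or intolerable.

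Section 1.1 schedules the HCS "at baseline (first visit), after the last TMS session, after the post-MRI". The schema in 1.2 repeats the baseline questionnaires, the HCS included, at Visit 4. The compensation table in 5.5 marks "Clinical Assessment & blood work" for the treatment day without naming a scale.

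On analysis, 8.1 applies LOCF to drop-outs and premature exits, whom it defines mainly as patients who stop before four sessions. Sections 6.4 and 9.3 restrict the analysis to patients who completed everything.

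**The concern.** The list in 7.1 is the only place that says what to record when stimulation stops early. It names two secondary scales and leaves out the primary one. The neighbouring sections disagree on whether the patient then goes on to Visit 4, where an HCS would otherwise be taken.

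At stake is the primary outcome of randomised patients who received some treatment and stopped, possibly because of tolerability or worsening. An HCS that is not taken at the time cannot be recovered later. The LOCF sentence makes this more than a gap in record-keeping. Under section 3 the baseline HCS is an assigned anchor of 10, not a measurement, so carrying it forward enters no change whatever happened to the voices.

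**Working it through.** **Inputs.** HCS baseline fixed at 10 and later range 0 to 20 (section 3); 20 patients per arm (9.2); LOCF for drop-outs and premature exits (8.1); completers only (6.4, 9.3); replacement of patients withdrawn after treatment (7.2). No rate of early stopping is given.

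**Step 1: the plan's own figure.** Section 9.2 assumes an effect size of 0.9, 80% power and alpha 5%; two-sided testing is my assumption. The normal approximation gives 2 × (1.960 + 0.842)² / 0.9² = 15.70 / 0.81 = 19.4, so 20 per arm and 40 in total. The stated figure is reproduced. The noncentral t calculation gives 20.39, or 21 per arm, and 79.2% power at 20 per arm. That small difference has no bearing here; 20 is used below only as a divisor.

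**Step 2: is a post-baseline HCS assured after a stop at session 1, 2 or 3?**

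| Text followed | HCS at stopping | HCS at Visit 4 |
|---|---|---|
| 7.1 | possible, not required | yes, through 1.2 |
| 1.1, 6.1.2, 8.3.5 (withdrawn) | possible, not required | not assured |
| 7.2 or 6.4, if used to remove the patient | possible, not required | not assured |

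The middle column is possible because 1.1 places an HCS after the last session and 5.5 shows a treatment-day assessment. It is not required because neither says what happens when session 4 is never given, and 5.5 does not name the HCS.

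**Step 3: if LOCF governs and no later HCS exists.**

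- Value carried forward = 10; imputed change = 10 − 10 = 0.
- Error for that patient = |true HCS − 10|. The smallest is 0; the largest is max(10 − 0, 20 − 10) = 10.
- Shift in the mean of an arm of 20 = 0/20 to 10/20, that is 0 to 0.50 points.
- If the patient is replaced under 7.2 and both are counted, the upper limit is 10/21 = 0.48.

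These are limits set by the scale for one patient, not estimates.

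**Step 4: if completers only governs.** The patient is left out, so the effect through LOCF is 0. The cost is a different one: a randomised and treated patient is excluded.

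**Step 5: which rule prevails?** The documents do not say. Section 6.4 gives a reason tied to the HCS, namely that all three ratings are needed. Sections 9.4.1 and 9.4.3 lean the same way for descriptive and secondary analyses. Section 8.1 nevertheless states LOCF without limiting it to any outcome.

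**The case against.** Read on its own terms, 7.1 may already cover the HCS. Its list need not be exhaustive, and it follows an instruction to complete the remaining procedures, which brings in Visit 4. The HCS due after the last session could also mean the last session received. This stands as far as it goes, and it is why the conclusion is "not assured" rather than "missing". It fails once the withdrawal wording in 1.1, 6.1.2 or 8.3.5 is followed.

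The conflict with 6.4 is softer. That section can be read as covering patients who decline the whole study, imaging and interviews included. This also stands; the clear conflict is with 1.1 and 6.1.2.

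All of the numerical effect runs through the LOCF sentence, which 6.4 and 9.3 contradict. This stands too: on the completers-only reading that effect is zero.

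A stopping HCS is not the same quantity as one after four sessions, since it reflects fewer sessions and an earlier time of day. This is fair, and the fix therefore records both.

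Stronger readings are tempting, but the documents do not support them:

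- A reader might infer that every early stopper lacks a post-baseline HCS. Sections 1.1, 1.2 and 5.5 leave room for one.
- A reader might infer that the voices go unmeasured. The BPRS subscale has a hallucination item and the BAVQ-R is taken, though neither can replace the HCS in the primary analysis.
- A reader might infer a distorted response rate, because an HCS of 10 fails the criterion of below 8. Section 9 plans no comparison of responder proportions, so that consequence attaches to no planned test.
- A reader might count the rule that antipsychotics end participation as part of the defect. It is deliberate, protects patients and is outside this point.

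**Conclusion.** The point holds and is minor. The 7.1 list omits the primary outcome, and 7.1 conflicts plainly with 1.1 and 6.1.2, with 8.3.5 for serious or intolerable events, and less clearly with 7.2 and 6.4. A post-baseline HCS for an early stopper is therefore possible but not assured.

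The size is conditional. With LOCF and no later HCS, each such patient is misstated by 0 to 10 points, at most 0.50 on the mean of an arm of 20. With completers only, the effect through LOCF is zero and the patient is lost to the randomised comparison. Neither figure is a forecast of bias in the trial, because the number of such patients is not given and may be zero.

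The textual finding rests on no assumption. The numerical limit assumes only the 0 to 20 scale, the anchor of 10 and 20 patients per arm.

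**What to change.** 1. Add an HCS by the blinded rater to the 7.1 list, with the time of rating and the number of sessions received. Take it at stopping, without delaying any medication that is needed.
2. Align 1.1, 6.1.2, 6.4, 7.2 and 8.3.5 with 7.1. A patient who stops rTMS, still consents, can safely continue and has had no antipsychotic should complete the Visit 4 HCS. The rule that antipsychotics end participation stays.
3. Do not carry the anchor of 10 forward as an outcome; change the LOCF sentence in 8.1 accordingly. Amend 6.4 and 9.3 so that treated patients with an observed post-baseline HCS are included. In 9.4.2, replace the repeated-measures ANCOVA, which in its usual form drops a patient with an incomplete set of ratings, by a model that accepts incomplete repeated measures, such as a mixed model. Keep the completers analysis as a sensitivity analysis. Report by arm how many patients have no post-baseline HCS.

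**Cost.** Parts 1 and 2 are one list item and consistent wording. The BPRS subscale and BAVQ-R are already taken at stopping, and section 3 describes the HCS as practical for daily use, so the burden is a few minutes of rating per early stopper. The rating will not always be feasible in an emergency, and it will reflect fewer sessions than planned. Part 3 is a larger change, because it alters the primary analysis set and model, and should be settled before outcome data are seen by arm. If only part 1 is adopted, the HCS taken at stopping is at least preserved for either analysis.

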7.2 PARTICIPANT DISCONTINUATION/WITHDRAWAL FROM THE STUDY

Participants are free to withdraw from participation in the study at any time upon request. Nevertheless, subjects may be prematurely terminated from the study if the investigators assess that the subject's clinical condition requires treatment(s) not available within the study context.

An investigator may discontinue or withdraw a participant from the study for the following reasons:

- Pregnancy as assessed with a pregnancy test before the two MRI measurements
- Significant study intervention non-compliance
- If any clinical adverse event (AE), laboratory abnormality, or other medical condition or situation occurs such that continued participation in the study would not be in the best interest of the participant
- Disease progression which requires discontinuation of the study intervention
- If the participant meets an exclusion criterion (either newly developed or not previously recognized) that precludes further study participation
- Participant unable to receive rTMS 4 times for one day
- If patients experience side effects that they are not willing to endure (such as headaches for example)
- Any medical condition which requires treatment with a medication with psychotropic effects
- Significant risk of suicidal or homicidal behavior (including aggressive behavior towards staff, others or themselves)
- MR Imaging contraindications
- Moving of patient or end of status as an in-patient at the Zucker Hillside Hospital

Duration of non-compliance will be determined by the trained study coordinator. Patients will be monitored closely by the study coordinator and all trained staff of the study. Changes i.e. in medication will be assessed before every visit/intervention.

If the patient had to have antipsychotics given because of an emergency or worsening of psychotic symptoms, then they are terminated from the study. However, we will also communicate on the ward that the patient's well-being is of main concern. Thus, should a patients' condition worsen and antipsychotics are thought to be the best help than medication should always be given regardless of the patient being enrolled in the study.

The reason for participant discontinuation or withdrawal from the study will be recorded on the Case Report Form (CRF). Subjects who sign the informed consent form and are randomized but do not

receive the study intervention may be replaced. Subjects who sign the informed consent form, are randomized, receive the study intervention, subsequently withdraw or are withdrawn or discontinued from the study will be replaced.

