4 STUDY DESIGN

4.1 OVERALL DESIGN

This is a randomized, placebo controlled, double-blind clinical trial. We aim to assess the efficacy of rTMS as a potentially beneficial treatment option in drug-naïve patients and patients refusing antipsychotic medication who suffer from AVH. We use a novel protocol with only one day of treatment including 4 sessions of low-frequency rTMS and compare the effects with the sham stimulation. Further, we aim to examine structural and functional neurophysiological characteristics as predictors for rTMS.

As primary outcome, we aim to examine the efficacy of low-frequency rTMS for AVH in patients with a schizophrenia spectrum disorder with regard to AVH based on the HCS. Further, Hallucination quality (BAVQ-R), hallucinations as a part of positive symptoms (BPRS-subscale), clinical global improvement (CGI), and general assessment of functioning (GAF) are secondary outcome measures. Structural and functional neurophysiological characteristics (rCBF, resting fMRI, T1, and DTI) are investigated as potential predictors for rTMS treatment response.

In order to achieve these aims, we will have two intervention arms: real and sham rTMS. Patients who are willing to take part in the study and declining treatment by antipsychotic medication to sufficiently treat psychotic symptoms will be randomly assigned by the (trained) research coordinator to either sham or real rTMS.

Subjects will be randomized using a permutation block design to real rTMS or sham rTMS treatment. Accordingly, a well-documented double-blind randomization plan will be developed by the study's biostatistician and implemented in collaboration with the investigator. Copies of the resulting permutation blocks and randomization codes will be kept by the unblinded research coordinator. Blinded study personnel will not have access to these codes. When a new subject is randomized to a particular group, the research coordinator will provide written notice of the randomization condition of the subject to the operator of the rTMS.

Double-blinding is ensured by the fact that the trained research assistant who is performing the rTMS treatments is not the same person (rater) who will conduct the psychopathology assessments. This allows the unbiased assessment of changes in AVH severity due to rTMS without the prior knowledge of the rater whether the patient received real or sham rTMS.

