9.2 SAMPLE SIZE DETERMINATION

This study aims to examine the efficacy of rTMS for the treatment of AVH in schizophrenia. To determine the effect of rTMS, this study uses an exploratory approach and should be considered a pilot study. If a treatment effect of rTMS (as compared to sham rTMS) would be detected, then this may serve as the basis for a follow-up study in a larger sample.

Previous meta-analyses (Aleman et al., 2007; Demeulemeester et al., 2012; Freitas et al., 2009; C. W. Slotema et al., 2014; C. W. Slotema et al., 2010; Tranulis et al., 2008) reported effect sizes ranging from 0.42 to 1.04 for LF rTMS over the left TPJ for the treatment of AVH. Based on this, we assume an effect size of 0.9 as a clinically meaningful effect to justify rTMS for the treatment of AVH compared to conventional antipsychotic medication. Following from this, we performed an *a priori* power analysis using the statistical software package R 3.1.3 and pwr.t.test (based on (Cohen, 1988)). With the assumed effect size of 0.9 and 80% power ($\alpha = 5\%$) we will have to recruit 40 patients in total, with 20 patients in the real rTMS and 20 patients in the sham rTMS group.

Considering the limited time frame of one year and based on the investigators' experience in the clinic about the number of subjects, we expect the aim of $N = 40$ to be feasible.

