9.3 POPULATIONS FOR ANALYSES

Data of all patients who attended pre-MRI and interview, 4 sessions of rTMS, and post-MRI and interview will be included in the analysis.

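### Treated patients who withdraw are excluded from the analysis and must be replaced, so the analysed groups are refilled for reasons that can depend on arm or outcome

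*Combined protocol and SAP*

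**What the plan says.** Section 7.2 separates two cases. Patients randomised but never treated are covered by a permissive rule: those who do not "receive the study intervention may be replaced". For patients already treated the rule is mandatory: those who "are randomized, receive the study intervention, subsequently withdraw or are withdrawn or discontinued from the study will be replaced".

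The reasons for leaving in the same section include side effects ("If patients experience side effects that they are not willing to endure (such as headaches for example"), adverse events, disease progression, and suicidal or homicidal risk. A separate paragraph adds: "If the patient had to have antipsychotics given because of an emergency or worsening of psychotic symptoms, then they are terminated from the study".

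The analysis rules remove these patients. Section 9.3: "Data of all patients who attended pre-MRI and interview, 4 sessions of rTMS, and post-MRI and interview will be included in the analysis". Section 6.4, on patients who do not finish: "The data collected up to this point will not be included in the analysis". Section 9.4.3 also leaves drop-outs out of the secondary analyses. No intention-to-treat set is defined. Section 8.1 points the other way and analyses drop-outs and premature exits by last observation carried forward (LOCF).

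On numbers, section 9.2 says "we will have to recruit 40 patients in total, with 20 patients in the real rTMS and 20 patients in the sham rTMS group", with no allowance for loss. On allocation, section 4.1 says "Subjects will be randomized using a permutation block design to real rTMS or sham rTMS treatment". Nothing says which code or arm a replacement receives.

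**The concern.** Randomisation makes the two groups comparable at the time of assignment. That protection is lost when patients leave the analysis for reasons arising after treatment and others take their places. If rTMS works, termination for worsening is plausibly more frequent on sham. If stimulation is uncomfortable, withdrawal for headache is plausibly more frequent on real rTMS. Each arm would then keep a differently selected set of patients, and the bias could run in either direction.

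Replacement adds two problems of its own. It restores the analysed count, so a completed dataset of about the planned size gives no sign of how many randomised patients are missing. It also leaves allocation undefined. The next code in the block list would not guarantee 20 per arm. Filling the withdrawn patient's arm would restore 20:20, but by a non-random assignment known in advance, which is incompatible with the concealment described in section 6.3.

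Section 9.2 says a detected effect may be the basis for a larger study, so a biased estimate would be carried forward.

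**Working it through.** **1. The plan's own figure.** Inputs from section 9.2: standardised effect 0.9, power 80%, alpha 5%, equal arms. The test is taken as two-sided, which the plan does not state. The normal approximation gives 2 × (1.960 + 0.842)² / 0.9² = 19.4, so 20 per arm and 40 in total, as stated. The exact t-test gives 20.4 per arm and 79.2% power at 20 per arm. Forty is therefore reproduced, and it contains nothing for loss. Replacement is the only device that keeps 20 completers per arm.

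**2. Which rule covers which patient.**
- *Leaves before four sessions:* excluded by 6.4 and 9.3, retained by LOCF under 8.1, and replaced under 7.2 if treated and withdrawn. If 8.1 governed, this patient and the replacement would both be analysed and the total would exceed 40. Section 3 sets baseline HCS at 10, so a patient with no later HCS would be carried forward as unchanged.
- *Completes four sessions, then leaves before the final assessment:* outside the 8.1 definitions, excluded by 9.3, replaced under 7.2.
- *Stops rTMS but stays in the study:* section 7.1 says the remaining procedures should be completed, yet 6.4 and 9.3 exclude the data.

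**3. Size when there is no treatment effect.** Assumptions, none of them in the documents: HCS SD 3; a fraction q of the real arm leaves and none of the sham arm; the leavers are those highest on a withdrawal tendency that has correlation r with HCS (higher is worse). The retained real-arm mean is then too low by r × 3 × φ(c) / (1 − q), where c is the upper-q normal quantile.
- q = 10%: 3 × 0.1755 / 0.90 = 0.58 at r = 1; 0.29 at r = 0.5.
- q = 15%: 3 × 0.2332 / 0.85 = 0.82 at r = 1; 0.41 at r = 0.5.

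False-positive rates by simulation (40,000 trials per setting, two-sided t-test at 5%):

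| r | q | False benefit (points) | Refilled to 20 | Not refilled |
|---|---|---|---|---|
| 0 | 10% or 15% | 0 | 5% | 5% |
| 0.5 | 10% | 0.29 | 6% | 6% |
| 0.5 | 15% | 0.41 | 7% | 7% |
| 1 | 10% | 0.58 | 9.5% | 8.9% |
| 1 | 15% | 0.82 | 14.7% | 13.0% |

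Equal loss of 10% in both arms gives no bias and a 5% rate.

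**4. Size when the treatment works.** Assume means of 10 on sham and 7.3 on real (difference 2.7 = 0.9 × 3), with anyone reaching HCS 13 excluded.
- Retained sham mean: 10 − 3 × 0.2420 / 0.8413 = 9.14.
- Retained real mean: 7.3 − 3 × 0.0656 / 0.9713 = 7.10.
- Observed difference: 2.04, about 24% below the true 2.7.

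The difference is the same with or without refilling. Power is about 68% refilled and 62% to 63% not refilled. Refilling takes about 3.8 sham and 0.6 real replacements.

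**5. Attribution.** In steps 3 and 4 the bias does not depend on refilling, so it comes from the exclusion. Refilling changes only the number analysed: it recovers some power in step 4 and slightly raises the false-positive rate in step 3 when bias is present.

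**The case against.** The strongest objection is that replacement is not the source of the bias. That is right. A reader might infer that section 7.2 alone distorts the comparison, but the same exclusions without refilling give nearly the same estimates.

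Other stronger readings also fail:
- *That most listed reasons reflect outcome.* Of the eleven in 7.2, pregnancy, MRI contraindications and moving or discharge are neutral, and several others are mixed.
- *That headache withdrawals must bias the result.* They do so only if they are related to HCS.
- *That exactly 40 will be analysed.* Section 9.2 says 40 are recruited; 40 completers is an inference from 7.2 read with 9.3.
- *That losses are concealed.* Section 7.2 requires the reason for withdrawal on the case report form. What is missing is a commitment to report all randomised patients by arm.
- *That same-arm filling is planned.* The plan is silent, and 6.3 says the coordinator does not know the next assignment.

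It can also be said that this is a self-described exploratory pilot with 3 to 4 days of participation, so few may leave. That limits the likely size. However, the patients are acutely ill and not taking antipsychotics, and one patient is 5% of an arm. The LOCF sentence in 8.1 does not settle the matter, because it conflicts with three other sections and misses patients who leave after the fourth session.

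**Conclusion.** The concern holds for the combination of rules. Mandatory replacement in 7.2, with the exclusions in 6.4, 9.3 and 9.4.3, lets post-treatment events decide which randomised patients are analysed and which are substituted. The exclusion produces the bias. Replacement refills the count, stands in for a loss allowance and leaves the new patient's arm undefined.

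The figures show a possible size and are not a forecast: a false benefit of about 0.3 to 0.8 points and a false-positive rate of about 6% to 15%, under SD 3, 10% to 15% loss in the real arm only, and correlation 0.5 to 1. Loss confined to sham would bias against rTMS by the same amount. Loss unrelated to outcome, or equal and similarly selected in both arms under the null, gives none. The documents do not support a claim about which direction will occur.

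**What to change.** 1. In 7.2, delete the replacement of patients who have received the intervention. State that anyone who received any rTMS or sham keeps the randomisation number, has outcomes collected where possible and is analysed in the assigned arm.
2. Amend 6.4, 9.3 and 9.4.3 to match, and reconcile them with 8.1 so that one stated rule handles missing HCS values, including for patients who leave after the fourth session. Deleting the 7.2 sentence alone would leave the bias and lower power.
3. If extra patients are wanted, enrol them only on the next unused block code, in addition to the withdrawn patient and never by same-arm filling.
4. Report all randomised patients and all withdrawals, with reasons, by arm.

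The withdrawal and medication rules are not changed.

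Cost: mainly wording, with slightly unequal arms possible. Without extras there may be fewer than 40 complete cases, and the stated 80% power should be restated. With completers only, power at effect size 0.9 is 77.0%, 74.6% and 69.3% for 5%, 10% and 20% loss. Planning for loss instead means randomising 40 / 0.95, 40 / 0.90 or 40 / 0.80, that is 43, 45 or 50 patients. These loss rates are assumptions.
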